### 3.2.9 Age at entry and age at first diagnosis

Age at entry into EP0034 will be given in years. For subjects with complete date of birth available, age at entry in to EP0034 will use the SDTM derivation definition in the analysis dataset.

For subjects without a complete date of birth available, age at entry into EP0034 will be calculated as:

Age at entry into the previous pediatric study + (number of calendar months between the informed consent dates of the previous pediatric study and EP0034)/12.

The age at entry into the previous pediatric study and date of birth are migrated from the previous pediatric study into the EP0034 SDTM.

The age at first diagnosis will be given in years and will be derived applying all rules for missing date imputation (see [Section 4.2.6](#)) with the following formula:

$$(\text{Date of first diagnosis of epilepsy} - \text{date of birth}) / 365.25$$

### 3.2.10 Weight band

Subjects will be classified as belonging to one of the following weight bands based on their weight at time of entry into study EP0034:

- <30kg
- $\geq 30$  to <50kg
- $\geq 50$ kg

### 3.2.11 Body mass index (BMI)

Body mass index (BMI) will be calculated using the formula:

$$\text{BMI} = \text{weight (kg)} / (\text{height [m]})^2$$

### 3.2.12 Enrollment groups

Subjects will be classified as belonging to one of the following enrollment groups for the purpose of disposition, demographic, and efficacy subgroup analyses:

- SP0967
- SP0969

### 3.2.13 Seizure frequency

Seizure frequency per 28 days (SF) will be based on the number of days (D) for which seizure information was provided:

$$\text{SF} = (\text{Number of seizures}) \times (28/D)$$

If a seizure cluster is reported, it will be assigned to the correct seizure type and the highest recorded daily number of seizures of that seizure type during the 28 days prior to the cluster event will be used as the imputed number of seizures for the day on which the cluster occurred. If no other seizures are recorded for that seizure type for the subject in the 28 days prior to the cluster event, the frequency will be set to 1.

If more than 1 cluster event occurred on the same day for Type II or Type III seizure, the seizure cluster will be assigned to the correct seizure type and the frequency for each cluster event will be set to the highest recorded daily number of seizures of that seizure type during the 28 days prior to the cluster event. If no other seizures are recorded for that seizure type for the subject in the 28 days prior to the cluster event, the frequency will be set to the number of cluster episodes reported.

If more than 1 cluster event occurred on the same day for Type I seizure, the seizure clusters will be assigned to the correct seizure type and overall frequency will be set to the maximum of:

- The highest recorded daily number of seizures of that seizure type during the 28 days prior to the cluster event
- The number of cluster episodes reported on that day

### 3.2.14 Percent change in seizure frequency

The percent change in seizure frequency per 28 days (PCH) from the Baseline value (B) (using the Baseline definition in [Section 3.3](#)) to the Treatment Period interval (T) is defined as:

$$PCH = [(SF_T - SF_B) / SF_B] \times 100$$

where  $SF_T$  corresponds to the seizure frequency during the Treatment Period for the relative interval in the open-label study and  $SF_B$  corresponds to the Baseline seizure frequency.  $(SF_T - SF_B)$  is defined as the absolute reduction in seizure frequency. The frequency for both periods will be standardized to the number of seizures per 28 days.

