### 2.2.3.3 Other efficacy variables

The following other efficacy variables will be computed for subjects from SP0969:

- Percentage of 50% responders (subjects with at least a 50% reduction in total partial-onset seizure frequency per 28 days compared to Baseline), with Baseline defined as the period before receiving LCM in the previous pediatric study
- Percentage of 50% responders per seizure type (simple partial, complex partial, or secondarily generalized) compared with Baseline
- Percentage of 75% responders (subjects with at least a 75% reduction in total partial-onset seizure frequency per 28 days compared to Baseline), with Baseline defined as the period before receiving study medication in the previous pediatric study
- Percentage of 75% responders per seizure type (simple partial, complex partial, or secondarily generalized) compared with Baseline
- Absolute and percent reduction in total partial-onset seizures and per partial-onset seizure type (simple partial, complex partial, or secondarily generalized) compared to Baseline
- Partial-onset seizure frequency per 28 days

The following other efficacy variables will be computed for all subjects in EP0034:

- Achievement of seizure-free status (no seizure) during the study for total partial-onset seizure and per seizure type (simple partial, complex partial, or secondarily generalized)

- Clinical Global Impression of Change
- Caregiver's Global Impression of Change
- Change from Baseline in Pediatric Quality of Life Inventory (PedsQL)
- Health care resource use: concomitant medications, medical procedures, health care provider consultations not foreseen by the protocol, and hospital stays

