### 3.2.15 Response to treatment

Response to treatment is based on the percent change in seizure frequency relative to Baseline (using the Baseline definition in [Section 3.3](#)). Subjects who experience at least a 50% reduction from Baseline will be considered  $\geq 50\%$  responders. Subjects who experience at least a 75% reduction from Baseline will be considered  $\geq 75\%$  responders.

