**Table 8–4: CBCL/6-18**

Syndrome scale	Items
Aggressive behavior	3, 16, 19, 20, 21, 22, 23, 37, 57, 68, 86, 87, 88, 89, 94, 95, 97, 104
Anxious/depressed	14, 29, 30, 31, 32, 33, 35, 45, 50, 52, 71, 91, 112
Attention problems	1, 4, 8, 10, 13, 17, 41, 61, 78, 80
Rule-breaking behavior	2, 26, 28, 39, 43, 63, 67, 72, 73, 81, 82, 90, 96, 99, 101, 105, 106
Social problems	11, 12, 25, 27, 34, 36, 38, 48, 62, 64, 79
Somatic complaints	47, 49, 51, 54, 56a, 56b, 56c, 56d, 56e, 56f, 56g
Thought problems	9, 18, 40, 46, 58, 59, 60, 66, 70, 76, 83, 84, 85, 92, 100
Withdrawn/depressed	5, 42, 65, 69, 75, 102, 103, 111

Standardized T-scores are determined for each subject’s raw syndrome and overall scores based on the subject’s age and sex. Tables mapping each raw score to the appropriate T-score are provided in the CBCL Professional Manual. Standardized T-scores determined from each subject’s raw syndrome scale scores will be reproduced programmatically using the appropriate scoring spreadsheets.

Raw scores and change from Baseline for each CBCL/1½-5 syndrome (aggressive behavior, anxious/depressed, attention problems, emotionally reactive, other problems, sleep problems, somatic complaints, and withdrawn) will be summarized for each visit, and Last Visit.

Raw scores and change from Baseline for each CBCL/6-18 syndrome (aggressive behavior, anxious/depressed, attention problems, rule-breaking behavior, social problems, somatic complaints, thought problems, and withdrawn/depressed) will be summarized for each visit, and Last Visit.

The Calculated T-scores, raw scores, and change from Baseline in raw scores will be listed.

A decrease from Baseline (change from Baseline <0) in the CBCL syndrome raw score will indicate improvement in behavior, while an increase (change from Baseline > 0) indicates worsening.

In addition, for both the CBCL/1½-5 syndrome and /6-18 syndrome, subjects will be categorized according to the Calculated T-score as follows:

- T-score is < 65 = “Normal”
- T-score is ≥ 65 = “Borderline or Clinical range (BCR)”

Summaries of shifts from Baseline to each post-Baseline visit, and from Baseline to Last Visit will also be provided based on the CBCL calculated T-score categories of Normal and BCR. The descriptive summaries of change from Baseline and shift summaries will be presented only when a corresponding Baseline value from the same questionnaire is available.

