### 9.1.5 Absolute and percent reduction in total partial-onset seizures

The following analyses will only be done for subjects who participated in SP0969.

Absolute and percent reduction from Baseline (as defined in [Section 3.2.14](#)) in total partial-onset seizures will be summarized by seizure time intervals (as defined in [Section 3.2.21](#)) and also for the entire Treatment Period. This will be repeated, separately by seizure type (simple partial, complex partial, or partial, secondary generalized).

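### SAP 3.2.14 and 9.1.5 apply the label reduction to a treatment-minus-Baseline quantity, so improvement prints as a negative reduction and worsening as a positive one

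*SAP*

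**What the plan says.** SAP 3.2.14 defines the percent change in seizure frequency as PCH = [(SF_T − SF_B)/SF_B] × 100. SF_T is the frequency per 28 days in the treatment interval, and SF_B "corresponds to the Baseline seizure frequency". The section then says that the numerator, SF_T − SF_B, "is defined as the absolute reduction in seizure frequency". It does not define a percent reduction.

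SAP 9.1.5 plans summaries of "Absolute and percent reduction from Baseline" for subjects who took part in SP0969, by seizure time interval, for the whole Treatment Period and by seizure type. It cites 3.2.14 as the definition of both quantities. The variable is listed in SAP 2.2.3.3 as "Absolute and percent reduction in total partial-onset seizures and per partial-onset seizure type", and protocol 4.2.3 names it the same way. Neither list gives a formula or a sign.

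SAP 3.2.15 covers responders: "Response to treatment is based on the percent change in seizure frequency relative to Baseline". The threshold is stated in words, as a reduction of at least 50% or at least 75%.

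**The concern.** Treatment minus Baseline is a change. A reduction is Baseline minus treatment. SAP 3.2.14 attaches the second name to the first expression. SAP 9.1.5 extends the mismatch to the percent version, because the only percent quantity its cross-reference can reach is PCH.

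The outputs affected are the tables for an efficacy variable named in the protocol. A programmer who follows the text exactly produces a table titled as a reduction in which negative entries are improvements. Someone reading that table without the SAP formula would take a negative mean or median reduction as worsening. SAP 3.1 requires the minimum and maximum for continuous variables, and these would also be read the wrong way round.

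Nothing else in the SAP corrects this. For the CBCL, SAP 8.4.8 states the direction: a decrease "in the CBCL syndrome raw score will indicate improvement in behavior". The BRIEF-P and BRIEF sections do the same. The seizure sections have no such statement, and none reverses the sign for display.

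**Working it through.** The plan gives no worked value for this variable, so there is no figure to reproduce. The check applies the SAP's expressions to example frequencies.

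**Inputs.** The two expressions come from SAP 3.2.14, and the pointer to them from SAP 9.1.5. The seizure frequencies per 28 days are illustrative assumptions; the signs do not depend on them.

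**Formulas.**
- As written: absolute = SF_T − SF_B; percent = PCH = (SF_T − SF_B)/SF_B × 100.
- As a reduction: absolute = SF_B − SF_T; percent = (SF_B − SF_T)/SF_B × 100 = −PCH.

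| SF_B | SF_T | As written, absolute | As written, percent | True reduction, absolute | True reduction, percent |
|---|---|---|---|---|---|
| 20 | 5 | −15 | −75 | +15 | +75 |
| 20 | 8 | −12 | −60 | +12 | +60 |
| 20 | 20 | 0 | 0 | 0 | 0 |
| 20 | 30 | +10 | +50 | −10 | −50 |
| 20 | 40 | +20 | +100 | −20 | −100 |
| 8 | 20 | +12 | +150 | −12 | −150 |

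For example, 20 to 8 gives 8 − 20 = −12 and −12/20 × 100 = −60. Going from 8 to 20 gives 20 − 8 = +12 and 12/8 × 100 = +150.

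**General sign.** For any SF_B > 0, SF_T − SF_B and PCH are negative exactly when the frequency falls and positive exactly when it rises. Since SF_T cannot be below zero, a true percent reduction cannot exceed 100. A printed percent reduction of +150 is therefore impossible on its face.

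**Minimum and maximum.** Take the three children with SF_B = 20 and SF_T = 5, 8 and 40. As written, the absolute reductions are −15, −12 and +20. The minimum, −15, belongs to the child who improved most, and the maximum, +20, to the child who worsened. As true reductions the values are +15, +12 and −20: the maximum, +15, is the child who improved most and the minimum, −20, is the child who worsened. The median moves from −12 to +12.

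**The case against.** The strongest reply is that this is one mislabelled term. SAP 3.2.14 is headed and worded as percent change, and as a percent change PCH has the correct sign. The word reduction becomes attached to the percent quantity only through the cross-reference in 9.1.5. The formula is explicit, so a reader who looks it up can recover the direction, and every magnitude is right. Post-minus-Baseline is also the direction the SAP uses for the CBCL and BRIEF scores. All of this stands, and it limits the size of the point. It does not remove it: the CBCL and BRIEF outputs are called change and come with a stated direction, whereas these are called reduction and have none.

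A reader might infer that children who worsen by 50% or more would be counted as responders, since 20 to 30 gives PCH = +50. The documents do not support that. SAP 3.2.15 ties response to percent change and, in the next sentence, requires a reduction from Baseline; in plain sense that is PCH ≤ −50, so 20 to 8 (PCH = −60) counts and 20 to 30 does not. Protocol 4.2.3, SAP 2.2.3.3 and SAP 9.1.3 describe responders the same way. All that can be said is that no signed cut-off is printed.

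A reader might also infer that wrongly signed values would be posted on a public registry. The SAP's registry statement, in 8.2, concerns adverse events only and does not mention this variable.

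**Conclusion.** The point holds as an error of label and sign. If SAP 3.2.14 and 9.1.5 are followed exactly, every subject whose seizure frequency changes from Baseline appears in the 9.1.5 tables with the opposite sign to the table's title, and the extremes swap meaning. This rests only on the two definitions and on SF_B being positive.

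The severity is minor. The variable is among the other efficacy variables; the secondary one is the percentage of seizure-free days. It is summarised descriptively, for SP0969 subjects only, and no hypothesis test or sample size depends on it. Responder results are not affected on the plain reading of 3.2.15.

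**What to change.** In SAP 3.2.14, define absolute reduction = SF_B − SF_T and percent reduction = (SF_B − SF_T)/SF_B × 100 = −PCH, and use these two quantities in 9.1.5. This keeps the variable name used in the protocol. With it, 20 to 8 prints as +12 and +60%, and 8 to 20 as −12 and −150%.

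An equally coherent alternative is to leave the formulas alone, title the 9.1.5 outputs absolute change and percent change, and add a note that negative values mean fewer seizures.

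As a clarification only, print the responder cut-offs in 3.2.15 as PCH ≤ −50 and PCH ≤ −75.

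The cost is about two lines of SAP text. No new data and no additional analysis are needed.

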### 3.2.15 Response to treatment

Response to treatment is based on the percent change in seizure frequency relative to Baseline (using the Baseline definition in [Section 3.3](#)). Subjects who experience at least a 50% reduction from Baseline will be considered  $\geq 50\%$  responders. Subjects who experience at least a 75% reduction from Baseline will be considered  $\geq 75\%$  responders.

### 3.2.16 Seizure day

A seizure day is defined as a day where any type of seizure was reported in the seizure diary and seizures were assessed. Days in the seizure diary which are marked as “not done” on the eCRF will not be counted as a seizure day.

### 3.2.17 Seizure-free day

A seizure-free day is defined as a day where no seizures were reported in the seizure diary and seizures were assessed. Days in the seizure diary which are marked as “not done” on the eCRF will not be counted as a seizure-free day.

### 3.2.18 Seizure-free status

Subjects will be considered seizure-free for a given period if the subject completes the period, reports zero seizures during the period, and has no more than 10% of days in the period for which seizure data is not available (ie, “not done” is noted on the Seizure Frequency eCRF module). Seizure diary days where “not done” has been reported for days when subjects were participating in a previous study will not be counted toward the 10% of days with missing seizure diary data (eg, missing seizure data due to a previous study will not count against a subject in the assessment of seizure-free status). If a subject enrolls in a short-term iv substudy, days of participation in the substudy will also not be considered in the assessment of seizure-free status.

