At the completion of the study, investigators should discuss treatment options with the subject and/or their legal representative(s) to best manage the subject's epilepsy. Taper of LCM may not be required for some subjects who complete the study, depending on the treatment option selected by the investigator in consultation with the subject and/or legal representative(s). These subjects should complete Visit 13/Termination Visit and then complete the Safety Follow-Up Telephone Contact 30 days (-1/+3 days) after the final dose of LCM. The Safety Follow-Up Visit is not required for subjects who complete the study and who do not undergo taper of LCM. The Safety Follow-Up Visit and the Safety Follow-Up Telephone Contact are not required for subjects who participate in EP0151 or EP0152.

Subjects who complete the study and discontinue use of LCM (as determined by the investigator in consultation with the subject and/or legal representative) should taper LCM gradually as described in Section 7.2.2. These subjects should complete Visit 13/Termination Visit and enter the Taper Period.

Subjects who prematurely discontinue the study should complete an Early Termination Visit. At the time of withdrawal from the study, investigators should discuss treatment options with the subject and/or their legal representative(s) to best manage the subject's epilepsy. Taper of LCM may not be required for some subjects who withdraw from the study prematurely, depending on the treatment option selected by the investigator in consultation with the subject and/or legal representative(s). These subjects should complete the Safety Follow-Up Telephone Contact 30 days (-1/+3 days) after the final dose of LCM.

Subjects who withdraw from the study prematurely and discontinue use of LCM (as determined by the investigator in consultation with the subject and/or legal representative) should taper LCM gradually as described in Section 7.2.2. These subjects should enter the Taper Period.

Taper Period

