The Taper Period (up to 4 weeks, depending on dose level achieved) will be required for subjects who complete the study or withdraw from treatment during the study if the following doses are achieved: LCM ≥ 3 mg/kg/day for subjects receiving oral solution, or LCM ≥ 150 mg/day for subjects taking tablets; lower doses will not require a taper (refer to Section 7.2.2). A Taper Visit must be completed at the end of the Taper Period. Taper of LCM may not be required for some subjects who complete the study or withdraw from the study prematurely, depending on the treatment option selected by the investigator in consultation with the subject and/or legal representative(s) or for subjects who participate in EP0151 or EP0152.

End of study and Safety Follow-Up Period

Subjects who complete the study or withdraw prematurely from the study, and who discontinue use of LCM, should complete a Safety Follow-Up Visit 2 weeks (± 2 days) after the final dose of LCM. A Safety Follow-Up Telephone Contact is required for all subjects (those who complete the study as planned or have withdrawn prematurely from the study). This telephone contact will occur 30 days (-1/+3 days) after the final dose of LCM. The Safety Follow-Up Visit and the

Safety Follow-Up Telephone Contact are not required for subjects who participate in EP0151 or EP0152.

Unscheduled visits may be conducted at the discretion of the investigator.

Detailed schedules of study procedures are provided in Section 5.2, and a study schematic diagram is included in Section 5.3.

No formal interim analysis or Data Monitoring Committee is planned.

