8 STUDY PROCEDURES BY VISIT

Detailed tabular schedules of study procedures are provided in Section 5.2.

A time window of ± 7 days relative to Visit 1 is applicable for all scheduled visits and telephone contacts after Visit 1 during the Treatment Period. On the mornings of the clinic visits, the subject should take the morning LCM dose at the usual time.

At all visits and telephone contacts, subjects will be instructed to call the investigator if any intolerable and/or serious AEs occur before the next visit or contact.

Subjects will be required to have a 12-lead ECG (2 interpretable recordings approximately 20 to 30 minutes apart) conducted at LCM maximum plasma concentration (C_{max}) 1 week after a LCM dose increase to ≥ 8 mg/kg/day, after subsequent dose increases (ie, the first time a subject reaches a LCM dose of 8mg/kg/day, 9mg/kg/day, 10mg/kg/day, etc) or for LCM doses of >400 mg/day (ie, the first time a subject reaches a LCM dose of 400mg/day, 500mg/day, etc), or when a new concomitant AED is introduced during the study. This ECG can be conducted at an Unscheduled Visit (Section 8.5), if necessary. Subjects having a LCM dose increase to ≥ 8 mg/kg/day or to ≥ 400 mg/day, or when a new concomitant AED is added will be required to arrive at the clinic prior to taking their morning dose of LCM. Subjects will be administered their morning LCM dose by study personnel at the clinic so that an ECG (2 interpretable recordings approximately 20 to 30 minutes apart prior to any blood sample collection or vital signs assessment) can be performed 30 minutes to 1 hour after the administration of LCM.

The PedsQL, the Achenbach CBCL, and the BRIEF-P and BRIEF will only be administered in countries where a validated translated version is available. The Bayley-III scales should be completed only for subjects enrolled in English-speaking countries.

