8.1.12 Visit 13/Termination Visit (Week 96)

Visit 13 (end of Week 96 \pm 7 days relative to Visit 1) will be the treatment Termination Visit for subjects who complete up to 2 years of treatment. Subjects who prematurely discontinue the study must return for an Early Termination Visit as soon as possible (Section 8.1.13).

At Visit 13/Termination Visit, the following will be performed:

- Concomitant medications assessment
- Concomitant AEDs assessment

-
- VNS assessment (if applicable)
 - Physical examination (complete)
 - Tanner Stage (only for subjects who are pubescent at Visit 1 or who enter puberty during the course of the study)
 - Blood pressure and pulse rate, including orthostatic assessments in ambulatory subjects
 - Body weight and height assessments
 - Head circumference
 - Neurological examination (complete)
 - 12-lead ECG (2 interpretable recordings, approximately 20 to 30 minutes apart, to be performed prior to any blood draws and vital signs assessment and, if possible, after the subject has been in a supine position for approximately 5 minutes preceding the ECG recording)
 - Blood sample for clinical chemistry and hematology
 - Blood sample for endocrinology
 - Urine sample for urinalysis (for subjects aged ≥ 5 years) (urine assessments will be based on the subject's ability to void and staff's ability to collect urine [in an appropriate container])
 - Serum pregnancy test (for female subjects of childbearing potential)
 - C-SSRS (for all subjects ≥ 6 years of age, the "Since Last Visit" version should be completed; if a subject becomes 6 years of age during the study, the "Already Enrolled" version should be used at the first visit at which the subject is 6 years of age and the "Since Last Visit" version at subsequent visits)
 - Clinical Global Impression of Change assessment
 - Caregiver's Global Impression of Change assessment
 - Achenbach CBCL (the CBCL/1½-5 for children from 1.5 to 5 years old and the CBCL/6-18 for children 6 years and older)
 - BRIEF-P (≥ 2 years to < 5 years of age)/BRIEF (≥ 5 years of age) assessment (version consistent with age at the visit)
 - PedsQL assessment (form consistent with age at the visit)
 - Contact IXRS (only if LCM will be dispensed for taper, as described below)
 - Review LCM return and compliance
 - Dispense LCM (if applicable for taper, as described below)
 - Reminder to complete subject diary on a daily basis
 - Adverse event reporting
 - Health care resource use

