### 3.2.5 Monthly time intervals

A month is defined as 28 days and time intervals based on monthly durations are defined as multiples of 28 days (eg, 12 months is defined as 336 days). The definition of 3-month intervals is based on the example durations in [Table 3–1](#) which use 28-day months where the date of the first dose of LCM is Day 1:

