### 3.2.19 Completer cohorts

A completer cohort will be defined as the subset of subjects in the Full Analysis Set (FAS) that were enrolled and treated with LCM for a specified duration of time. For example, a 6-month completer cohort consists of subjects enrolled and treated with LCM for at least 6 months where a month is defined as 28 days.

Subjects will be classified as belonging to one of the following completer cohorts for the purpose of subgroup analyses:

- 6 months
- 12 months
- 18 months
- 24 months

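### The 24-month completion cut-off falls on the nominal Visit 13 date with no allowance for the visit window, and the ≥24 months seizure interval holds either a few days or mostly taper days

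*SAP*

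**What the plan says.** SAP 3.2.5: "A month is defined as 28 days and time intervals based on monthly durations are defined as multiples of 28 days". Its worked example puts 12 months at 336 days.

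SAP 3.2.19 defines completer cohorts at 6, 12, 18 and 24 months. Its example is that the 6-month cohort "consists of subjects enrolled and treated with LCM for at least 6 months where a month is defined as 28 days".

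SAP 3.2.18, on seizure-free status: "Subjects will be considered seizure-free for a given period if the subject completes the period, reports zero seizures during the period". The only allowance is that up to 10% of diary days may be missing. It does not say what completing a period means.

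Protocol 8.1.12 places Visit 13 at Week 96; it "will be the treatment Termination Visit for subjects who complete up to 2 years of treatment". Protocol 8 gives a window of ± "7 days relative to Visit 1 is applicable for all scheduled visits and telephone contacts after Visit 1 during the Treatment Period", and adds: "On the mornings of the clinic visits, the subject should take the morning LCM dose at the usual time".

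On taper, Protocol 5.1 says: "The Taper Period (up to 4 weeks, depending on dose level achieved) will be required for subjects who complete the study or withdraw". It also says: "Taper of LCM may not be required for some subjects who complete the study". SAP 3.2.1.1 takes the last dose to be the last one in the study. SAP 3.2.7 counts exposure from first to last dose, and SAP 3.2.2 ends the Treatment Period at the later of last dose and Termination Visit. Taper days therefore fall inside the Treatment Period.

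The last two seizure intervals in SAP 3.2.21 are >18 to ≤24 months and ≥24 months. SAP 9.1.3 classifies response in an interval for any subject with seizure data in it and sets no minimum number of days.

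**The concern.** The last cut-off sits on a visit that may legitimately fall a week either side of it. Entry to the 24-month cohort then depends partly on which day in the window Visit 13 took place. If taper doses count as treatment, entry also depends on whether the subject tapered. If completing a period means reaching Day 672, the same early-seen subject cannot be seizure-free for >18 to ≤24 months either, even with a perfect diary up to Visit 13.

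The ≥24 months interval is a separate problem. It begins where planned treatment ends, so its response rates rest on very few on-treatment days, or on days of falling dose.

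These are the longest-term seizure results of a 2-year extension. Affected are the 24-month cohort row of seizure-free status in SAP 9.1.6 (including the whole-Treatment-Period result, which is shown by cohort), the last seizure-interval rows, and the ≥24 months disposition count in SAP 5.1, which uses the same 28-day cut-off.

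**Working it through.** **Inputs.** Month of 28 days (SAP 3.2.5). Visit 13 at Week 96, ±7 days (Protocol 8 and 8.1.12). Duration = last dose date − first dose date + 1 (SAP 3.2.7). Standard taper of 2 to 4 weeks by dose reached (Protocol 7.2.2). Assumed: first dose on the Visit 1 date (Day 1), and last dose of a non-tapering completer on the Visit 13 date. Let k be the offset of Visit 13 from Week 96, in days.

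**1. The cut-off.** 12 × 28 = 336 reproduces the SAP's example. 24 × 28 = 672 = 96 × 7.

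**2. Completers who do not taper.** Duration = 672 + k + 1 = 673 + k.
- k = −7: 666 days; k = −2: 671; k = −1: 672; k = 0: 673; k = +7: 680.
- Below 672 for k = −7 to −2, which is 6 of 15 window days (40%).
- If one dose date shifts by a day, duration = 672 + k (665 to 679). Then k = −7 to −1 fall short, 7 of 15 (47%).
- With assumed normal visit scatter (rounded, truncated at ±7) and SD of 2, 3 or 4 days, 23%, 31% or 34% fall short. With the one-day shift the shares are 40%, 43% and 45%.

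**3. If taper doses count.** Earliest in-window visit plus a 2-week taper: 666 + 14 = 680, so the subject qualifies. A withdrawer on day d with a 28-day taper qualifies if d + 28 ≥ 672, that is d ≥ 644, without reaching Visit 13.

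**4. Seizure-free status for >18 to ≤24 months.** The interval is 6 × 28 = 168 days. The 10% rule tolerates 16 missing diary days (0.10 × 168 = 16.8). It does not cover completion, which is a separate condition.

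**5. Length of the ≥24 months interval.** If E is the last day, the length is E − 672 counted from Day 673, or E − 671 counted from Day 672.

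| Case | E | Days |
|---|---|---|
| No taper, on schedule | 673 | 1 to 2 |
| No taper, latest in window | 680 | 8 to 9 |
| 4-week taper, on schedule | 701 | 29 to 30 |
| 4-week taper, latest in window | 708 | 36 to 37 |

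Taper share with a 4-week taper: on schedule 28/30 = 93% or 28/29 = 97%; at the latest visit 28/37 = 76% or 28/36 = 78%.

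**6. What a short interval does to response (illustration).** Assume the true rate is unchanged, Baseline is known exactly and counts are Poisson with mean μ = rate × D/28. The probability of an apparent ≥50% reduction is P(count ≤ μ/2).

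| Rate per 28 days | D = 8 | D = 9 | D = 29 | D = 36 | D = 168 |
|---|---|---|---|---|---|
| 2 | 0.57 | 0.53 | 0.39 | 0.27 | 0.05 |
| 4 | 0.32 | 0.28 | 0.22 | 0.11 | 0.005 |
| 10 | 0.22 | 0.17 | 0.06 | 0.03 | <0.001 |
| 20 | 0.08 | 0.12 | 0.01 | 0.002 | <0.001 |

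The values are not smooth in D because counts are whole numbers. At rate 4 with variance twice the mean, the probability is 0.41 at 9 days, 0.20 at 37 and 0.03 at 168. The documents give no Baseline rate, so all rates here are assumptions.

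**The case against.** **The cohort is defined by treated duration, not by attending Visit 13.** On that definition, leaving out a subject with 670 days and admitting a Day 644 withdrawer who tapered for 28 days is simply the rule at work. This is fair as far as it goes. But SAP 3.2.19 does not cite SAP 3.2.1.1 or 3.2.7, so whether taper days count is not settled. A cohort called completers that can exclude a subject who finished the study in window needs a stated reason.

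**The missing minimum of diary days is a general gap.** A subject withdrawing on Day 90 has 6 days in >3 to ≤6 months (Days 85 to 90) and is classified too. This stands. The last interval differs in that no in-window completer can have more than 8 to 9 days there without taper.

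**Stronger readings a reader might infer.**
- That the ≥24 months interval is too short for everyone. With a 4-week taper it can reach 36 to 37 days, and at 10 or 20 seizures per 28 days the false-response probability at 36 days is only 3% or 0.2%. For those subjects the difficulty is mainly what the days represent.
- That Day 672 certainly belongs to two intervals. Table 3–1 in SAP 3.2.5 ends each interval on the boundary day and starts the next one a day later, which suggests a start at Day 673. The ≥ sign, repeated in SAP 8.2, looks like a labelling slip.
- That 40% of completers are lost. The figure is a share of window days and applies only to completers who do not taper.

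**Conclusion.** The point holds and is minor. A stated rule excludes some protocol-compliant, non-tapering completers from the 24-month cohort: those seen 2 to 7 days early, or 1 to 7 days early if one dose date shifts by a day. This rests on dosing on the visit dates. The loss of seizure-free status for >18 to ≤24 months holds only if completion means reaching Day 672. The dependence on taper holds only if taper doses count as treatment. The ≥24 months response row is uninformative without taper and describes mostly taper days with a 4-week one; that response analysis concerns SP0969 subjects only.

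The secondary variable over the overall Treatment Period is not affected. Nor are the 6-, 12- and 18-month cohorts, whose cut-offs do not coincide with the end of planned treatment.

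A reader might infer that the 24-month seizure-free percentage is biased one way. The documents do not support this: the excluded subjects may or may not be seizure-free, and SAP 9.1.6 does not state the denominator of the by-interval table. Nor can the number affected be derived, because neither the visit scatter nor the share of non-tapering completers is given. Nothing is tested, and SAP 4.2.5 notes that efficacy is not the primary objective.

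**What to change.** 1. In SAP 3.2.18 and 3.2.19, define 24-month completion, and completion of >18 to ≤24 months, as at least 672 days of treatment or Visit 13 completed within its protocol window. State whether taper days count. Apply the same definition to the ≥24 months disposition category in SAP 5.1, or footnote the difference, so that the cohort and disposition counts can be reconciled.
2. In the seizure tables, drop the ≥24 months row and list those data. Fold on-treatment days after Day 672, up to Visit 13, into >18 to ≤24 months.
3. Wherever a last interval is kept in SAP 3.2.21 or 8.2, relabel it >24 months.

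The cost is SAP wording and minor programming. The downside is that some 24-month completers will have up to about 7 days fewer than 672 (672 − 665 = 7 at the earliest in-window visit with one dose date shifted; 6 otherwise).
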